#### 10.2.2 Skin Pain Numerical Rating Scale

The skin pain NRS is a patient-administered, 11-point horizontal scale anchored at 0 and 10, with 0 representing "no pain" and 10 representing "worst pain imaginable." Overall severity of a participant's skin pain is indicated by selecting the number that best describes the worst level of skin pain in the past 24 hours.

The item will be completed at each visit via an application on an electronic device in the clinic or the patient's own electronic device from baseline through Week 20.

#### **10.2.3** Sleep Disturbance Numerical Rating Scale

The sleep disturbance NRS is a scale used by the patients to report their degree of sleep loss related to AD. Patients will be asked the following question in their local language: how would you rate your sleep last night? On a scale of 0 to 10, with 0 being "no sleep loss related to signs/symptoms of AD" and 10 being "I cannot sleep at all because of the signs/symptoms of AD". Higher scores indicate worse outcomes.

The item will be completed at each visit via an application on an electronic device in the clinic or the patient's own electronic device from baseline through Week 20.

#### **10.2.4 Patient Oriented Eczema Measure**

The POEM is a 7-item, validated questionnaire completed by the patient to assess disease symptoms. Patients are asked to respond to questions on frequency of sleep loss and skin dryness, itching, flaking, cracking, bleeding, and weeping over the past week. All answers carry equal weight, with a total possible score ranging from 0 to 28. A high score is indicative of a poor quality of life.

The item will be completed at each visit via an application on an electronic device in the clinic or at the patient's own electronic device from baseline through Week 20 except Week 1.

#### 10.2.5 Patient Global Impression of Severity Scale

The PGIS scale is a single question asking the patient how he or she would rate his or her overall AD symptoms over the past 24 hours. The 5 categories of responses are (0) "no symptoms", (1) "very mild", (2) "mild", (3) "moderate", and (4) "severe."

The item will be completed at each visit via an application on an electronic device in the clinic or the patient's own electronic device from baseline through Week 20 except Week 1.

## 10.2.6 Patient Global Impression of Change Scale

The PGIC scale measures change in clinical status of AD. The PGIC is based on a 7-point scale, and the patient will rate the change from the start of treatment as 1 "very much improved," 2 "much improved," 3 "minimally improved," 4 "no change," 5 "minimally worse," 6 "much worse," and 7 "very much worse."

The item will be completed at each visit via an application on an electronic device in the clinic or the patient's own electronic device from baseline through Week 20 except Week 1.

## 10.2.7 Dermatology Life Quality Index

The DLQI is a 10-item validated questionnaire completed by the patient and used to assess the effect of skin disease on the patient's quality of life during the previous week. The 10 questions cover the following topics: symptoms; embarrassment; interference with shopping and home care, clothing choices, social and leisure activities, sports participation, work or study, close relationships, and sex; and treatment. Each question is scored from 0 to 3 ("not at all," "a little," "a lot," and "very much," respectively), giving a total score ranging from 0 to 30. A high score is indicative of a poor quality of life.

The item will be completed at each visit via an application on an electronic device in the clinic or the patient's own electronic device at baseline and Weeks 8, 16, and 20.

#### 10.2.8 Pulmonary Status Numerical Rating Scale in Patients with Asthma

Pulmonary disease status will be assessed in patients with asthma using a horizontal NRS. Patients will be asked to assess their "symptoms due to asthma over the past 7 days" on an NRS anchored by the terms (0) "no symptoms" and (10) "very bad symptoms".

The item will be completed at each visit via an application on an electronic device in the clinic or the patient's own electronic device at baseline and Weeks 4, 8, 12, 16, and 20.

# 11 SAFETY ASSESSMENTS

Safety assessments (medical history, vital signs and body weight, physical examinations, ECGs, clinical laboratory results [routine hematology, urinalysis and biochemistry], HADS, C-SSRS, and AEs) are to be performed at protocol-specified visits, as specified in the Schedule of Assessments (Table 4).

## **11.1 Medical History**

Medical history will be recorded at Screening. Investigators should document the occurrence, signs, and symptoms of the patient's pre-existing conditions, including any psychiatric treatment or hospitalization, covering all prior significant illnesses up to and including 6 months before screening. Additional pre-existing conditions present at the time when informed consent is given, and up to the time of first dosing (Visit 1), are to be regarded as concomitant. Medical history will include medications, alcohol consumption and smoking history, if applicable.

Illnesses first occurring or detected during the study, and/or worsening of a concomitant illness during the study, are to be documented as AEs on the eCRF in accordance with Section 11.8.1. All changes not present at Baseline or described in the past medical history (last 6 months) and identified as clinically noteworthy must be recorded as AEs.

Additionally, demographic data will be collected for all patients and include date of birth or age according to applicable regulations, sex, ethnicity, etc.

#### 11.2 Vital Signs and Body Weight

Vital signs (body temperature [measured in the ear], respiration rate, heart rate, and systolic and diastolic blood pressure measurements) will be evaluated at the visits indicated in the Schedule of Assessments (Table 4). All vital signs will be measured after the patient has been resting in a sitting position for at least 5 minutes. Blood pressure measurements are to be taken in the same arm for the duration of the study. Body weight (without shoes) will be recorded whenever vital signs are recorded; height (without shoes) will be recorded at Baseline only. A weight reduction of least 5% from baseline should be reported as a TEAE.

Vital sign measurements will be repeated if clinically significant or machine/equipment errors occur. Out-of-range blood pressure, respiratory rate, or heart rate measurements will be repeated at the Investigator's discretion. Any confirmed, clinically significant vital sign measurements must be recorded as AEs on the eCRF.

# **11.3** Physical Examination

A complete physical examination (a check of the head, eyes, ears, nose, and throat; heart; lungs; abdomen; skin; cervical and axillary lymph nodes; and neurological and musculoskeletal systems) will be performed at Screening (Visit 1) and Week 16. A limited physical examination will be conducted at Day 1 and Weeks 4, 8, 12, and 20 to verify continued patient eligibility and

to follow-up regarding any change in medical history. Physical examinations will be performed by a physician at the visits indicated in the Schedule of Assessments (Table 4).

## 11.4 Electrocardiograms

A 12-lead, resting ECG will be conducted at the visits indicated in the Schedule of Assessments (Table 4).

At Screening, the Investigator will examine the ECG traces for signs of cardiac disease that could exclude the patient from the study. An assessment of normal or abnormal results will be recorded; if the ECG is considered abnormal, the abnormality will be documented on the eCRF, and the ECG will be repeated if clinically significant abnormalities are observed or artifacts are present.

#### 11.5 Laboratory Assessments

Laboratory assessment samples (Table 5) are to be obtained at designated visits as detailed in the Schedule of Assessments (Table 4).

Hematology	Serum Chemistry				
Full and differential blood count	Albumin				
Hct	ALT				
Hb	ALP				
МСН	AST				
MCHC	BUN				
MCV	Creatinine				
Platelet count	Electrolytes (sodium, potassium, chloride, calcium,				
RBC count (% reticulocytes)	phosphorus)				
WBC count with differential (neutrophils,	GGT				
lymphocytes, monocytes, eosinophils, and basophils)	LDH				
	Total bilirubin				
	Direct bilirubin				
	Total IgE				
Other Screening Tests	Urinalysis (Dipstick)				
HIV antibody	Appearance				
HBV	pH				
HCV	Protein				
HCV RNA	Glucose				
HBsAg	Ketone bodies				
HBcAb	Indicators of blood and WBCs				
HBsAb	Specific gravity				
FSH (confirmatory test for female patients in a	Urine hCG (premenopausal females only)				
postmenopausal status defined as cessation of menses	Urobilinogen				
for at least 12 months without an alternative medical					
cause)					
Pregnancy test: A serum pregnancy test will be perform	ed on all WOCBP at Screening, and a urine pregnancy				
test will be performed at all other visits as indicated in Table 4.					

#### **Table 5. Laboratory Assessments**

Abbreviations: ALP, alkaline phosphatase; ALT, alanine aminotransferase; AST, aspartate aminotransferase; BUN, blood urea nitrogen; FSH, follicle-stimulating hormone; GGT, gamma-glutamyl transpeptidase; Hb, hemoglobin; HBcAb, hepatitis B core antibody; HBsAb, hepatitis B surface antibody; HBsAg, hepatitis B surface antigen; HBV, hepatitis B virus; hCG, human chorionic gonadotropin; Hct, hematocrit; HCV, hepatitis C virus; IgE, Immunoglobulin E; LDH, lactate dehydrogenase; MCH, mean corpuscular hemoglobin; MCHC, mean corpuscular hemoglobin concentration; MCV, mean corpuscular volume; RBC, red blood cell; WBC, white blood cell; WOCBP, women of childbearing potential.

Blood and urine samples will be analyzed at a central laboratory facility. Urine samples will be analyzed by dipstick at clinical site, and a microscopic analysis will be performed if the results of dipstick indicate abnormalities to be further investigated. All laboratory reports must be reviewed, signed, and dated by the investigator. A legible copy of all reports must be filed with both the patients' eCRF and medical record (source document) for that visit. Any laboratory test result considered by the Investigator to be clinically significant should be considered an AE (clinically significant AEs include those that require an intervention). Clinically significant abnormal values occurring during the study will be followed up until repeat test results return to normal, stabilize, or are no longer clinically significant.

#### 11.6 The Hospital Anxiety and Depression Scale

The HADS is a PRO, comprises 7 questions for anxiety and 7 questions for depression, with each answer being graded from 0 to 3 with a higher score indicating a worse condition. For each group of questions, scores of 7 or less indicate cases without anxiety or depression, whereas scores of 8 to 10, 11 to 14, and 15 to 21 indicate mild, moderate, and severe cases, respectively. The HADS is one of the tools recommended by the National Institute for Health and Care Excellence for diagnosis of depression and anxiety.

Any patient with a score for depressive symptoms  $\geq 15$  at baseline will not be eligible for enrollment in the study. Patients with a clinically significant worsening of depressive symptoms or new occurrence of clinically significant depression during the study may be referred to a mental health specialist (psychiatrist or clinical psychologist) for further evaluation. After a mental health specialist evaluation, the final decision on restarting or permanently discontinuing study treatment will be at the discretion of the Investigator in consultation with the mental health specialist. These cases should be reported as an AESI. Refer to Section 11.8.2.

#### 11.7 The Columbia-Suicide Severity Rating Scale

The C-SSRS, Investigator-administered version, was designed to provide a prospective, standardized measure of suicidality. The scale allows clinicians and researchers alike to assess the severity and lethality of suicidal behaviors and ideations and can be used to monitor treatment outcomes and establish suicide risk in a variety of research and clinical settings. Requiring approximately 5 minutes for completion, the C-SSRS is administered in the form of a clinical interview.

This C-SSRS is available in 2 versions: 1 for use at screening referring to the past year and 1 for use throughout the rest of the study referring to the time since the prior visit.

If at screening or baseline there are "yes" answers on item 4 or 5, the patient will not be included in the study.

Any patient with a positive response at subsequent visits (answers "yes" to questions 1-5) should be referred to a mental health specialist (psychiatrist or clinical psychologist) for further evaluation, and the study medication should be paused. After a mental health specialist evaluation, the final decision on restarting or permanently discontinuing study treatment will be at the discretion of the Investigator in consultation with the mental health specialist. These cases should be reported as an AESI. Refer to Section 11.8.2.

## 11.8 Adverse Events

AEs will be collected throughout the study as shown in the Schedule of Assessments (Table 4).

## 11.8.1 Adverse Events

An AE is any symptom, physical sign, syndrome, or disease that either emerges during the study or, if present at screening, worsens during the study, regardless of the suspected cause of the event. All medical and psychiatric conditions (except those related to the indication under study) present at screening will be documented in the medical history eCRF. Changes in these conditions and new symptoms, physical signs, syndromes, or diseases should be noted on the AE eCRF during the rest of the study. Clinically significant laboratory abnormalities should also be recorded as AEs. Surgical procedures that were planned before the patient enrolled in the study are not considered AEs if the conditions were known before study inclusion; the medical condition should be reported in the patient's medical history.

Any AEs that occur before dosing at Baseline will be categorized as pretreatment events. TEAEs will be defined as those AEs that occur or worsen in severity after initial dosing and up to 7 days after the last dose of study drug.

Patients will be instructed to report AEs at each study visit. All AEs are to be followed up until resolution or a stable clinical endpoint is reached.

Each AE is to be documented on the eCRF with reference to date of onset, duration, frequency, severity, relationship to study drug, action taken with study drug, treatment of event, and outcome. Furthermore, each AE is to be classified as being serious or nonserious. Changes in AEs and resolution dates are to be documented on the eCRF.

For the purposes of this study, the period of observation for collection of AEs extends from the time the patient gives informed consent until the follow-up visit. Follow-up of the AE, even after the date of therapy discontinuation, is required if the AE persists until the event resolves or stabilizes at a level acceptable to the investigator.

When changes in the intensity of an AE occur more frequently than once a day, the maximum intensity for the event should be noted. If the intensity category changes over a number of days, then those changes should be recorded separately (with distinct onset dates).

All AEs must be graded by using the National Cancer Institute Common Terminology Criteria for Adverse Events (CTCAE) grading system version 5.0 (CTCAE- Version 5.0) with reference to the unique clinical descriptions of severity for each AE in the guidance document. Please see Table 6 for selected unique clinical descriptions of severity of AEs. Only if an AE is not uniquely described in the CTCAE grading system, the general guidance for classification is to be used. Please see Table 7 for the general guideline for classification.

If a patient experiences a TEAE assessed as Grade 3 or higher using the unique clinical descriptions of severity (Grade 2 or higher for the SOC of cardiac disorders) according to CTCAE version 5, the patient should be permanently discontinued from the study drug and not receive additional doses.

Specific guidelines for classifying AEs by intensity are given in Table 6 and Table 7 and relationship to study drug are given in Table 8.

CTCAE Term	Grade 1	Grade 2	Grade 3	Grade 4	Grade 5
Diarrhea	Increase of <4 stools per day over baseline; mild increase in ostomy output compared to baseline	Increase of 4 - 6 stools per day over baseline; moderate increase in ostomy output compared to baseline; limiting instrumental ADL	Increase of >=7 stools per day over baseline; hospitalization indicated; severe increase in ostomy output compared to baseline; limiting self care ADL	Life-threatening consequences; urgent intervention indicated	Death
Nausea	Loss of appetite without alteration in eating habits	Oral intake decreased without significant weight loss, dehydration or malnutrition	Inadequate oral caloric or fluid intake; tube feeding, TPN, or hospitalization indicated	-	-
Vomiting	Intervention not indicated	Outpatient IV hydration; medical intervention indicated	Tube feeding, TPN, or hospitalization indicated	Life-threatening consequences	Death

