12.1. Adverse Events

AEs for all patients in the safety population will be included in the AE summaries.

Adverse events will be summarized by system organ class (SOC) and preferred term (PT) for each treatment and Orismilast total, based on the MedDRA dictionary version 24.0. Severity of AEs will be graded according to National Cancer Institute (NCI) Common Terminology Criteria for Adverse Events (CTCAE) version 5.

Any AEs that occur before dosing on study Baseline will be categorized as pretreatment events. TEAEs will be defined as those AEs that occur or worsen in severity after initial dosing and up to 7 days after the last dose of study drug.

Duration will be calculated for AEs that resolve as the difference between the resolution date and onset date plus 1 and expressed in days.

The summary tables will include the number of patients and the number of events. Percentages will be based on the number of patients in the safety population. For summaries by SOC and PT, a patient will be counted once at the SOC level and once at each PT within the SOC level.

For summaries by SOC, PT, and maximum severity, a patient will be counted once at the highest severity level for which the event occurred at the SOC level and the highest severity level for each unique PT within that SOC level. Therefore, patients may only contribute once to each PT and once to each SOC level.

The summaries presenting frequency of AEs by SOC and PT will be ordered by Orismilast total descending frequency of SOC and then, within a SOC, by Orismilast total descending frequency of PT.

The following tables will be provided:

- An overall summary of the number of events and number and percentage of patients reporting TEAEs, related TEAEs (TEAEs recorded as "Relationship to study drug" = "Possibly" or Probably" or "Definitely"), serious TEAEs (TESAEs), TEAEs resulting in death, TEAEs of special interest, TEAEs leading to study drug discontinuation, TESAEs leading to study drug discontinuation, TEAEs by relationship and TEAEs by toxicity grade (including exposure adjusted incidence rates [EAIR]);.A similar summary will be presented starting within the dose titration period (initial 3 weeks)." (without EAIR).
- TEAEs overall by system organ class and preferred term (including EAIR);
- TEAEs overall by system organ class and preferred term starting within the dose titration period (initial 3 weeks)
- TEAEs by maximum toxicity grade, overall and by system organ class and preferred term;

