- TEAEs by toxicity grade, overall and by system organ class and preferred term;

- TEAEs by maximum relationship to study medication, overall and by system organ class and preferred term;
- TEAEs by relationship to study medication, overall and by system organ class and preferred term;
- TEAEs leading to study drug discontinuation, overall and by system organ class and preferred term;
- TEAEs leading to study drug discontinuation, overall and by body weight at baseline system organ class and preferred term;
- TEAEs leading to study drug discontinuation, overall and by region, system organ class and preferred term; TEAE coded by MedDRA preferred term as diarrhoea, nausea, headache, dizziness and vomiting by time of onset of event;
- TEAEs of special interest, overall and by system organ class and preferred term;
- AEs starting in the 4-week Follow-up period overall by system organ class and preferred term;
- SAEs starting in the 4-week Follow-up period overall and by system organ class and preferred term;

Only TEAEs will be included in the summary tables, however separate listings for treatment-emergent AEs, non-treatment-emergent AEs, AEs starting within the dose titration period (initial 3 weeks), and AEs starting in the 4-week Follow-up period will be generated. Additional listings will be provided for deaths, AESIs, serious AEs, and AEs Leading to Study Drug Discontinuation.

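### The protocol splits an adverse event whose intensity changes over days into separately dated records, and SAP 12.1 has no rule to link them, so event counts and onset-based AE tables are undefined

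*Protocol*

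**What the plan says.** Protocol 11.8.1 has two recording rules for an AE whose intensity varies. Within a day: "When changes in the intensity of an AE occur more frequently than once a day, the maximum intensity for the event should be noted". Over longer periods: "If the intensity category changes over a number of days, then those changes should be recorded separately (with distinct onset dates". The second rule does not distinguish a worsening from an improvement. The same section defines a TEAE as an AE that begins or gets worse after the first dose and no later than 7 days after the last, and SAP 12.1 repeats that definition.

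SAP 12.1 then sets the reporting units: "The summary tables will include the number of patients and the number of events". It does not say what one event is in terms of eCRF records. On duration: "Duration will be calculated for AEs that resolve as the difference between the resolution date and onset date plus 1 and expressed in days". Several planned outputs depend on start date:

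- TEAEs starting in the titration period, which the SAP takes as the initial 3 weeks;
- "TEAE coded by MedDRA preferred term as diarrhoea, nausea, headache, dizziness and vomiting by time of onset of event";
- "AEs starting in the 4-week Follow-up period overall by system organ class and preferred term", with a matching SAE table.

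The section also plans TEAEs by each toxicity grade alongside TEAEs by maximum grade, and exposure-adjusted incidence rates with no formula.

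Patients, unlike events, do have a counting rule. In the ordinary incidence tables, "a patient will be counted once at the SOC level and once at each PT within the SOC level". The maximum-severity tables have their own version: "Therefore, patients may only contribute once to each PT and once to each SOC level". Neither document says how records of the same AE are joined. SAP section 21 places the table shells in a separate document.

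**The concern.** The recording rule and the analysis plan do not meet. The protocol creates several dated records from one illness episode. The SAP counts events, measures duration and assigns AEs to periods by onset date, without saying whether its unit is the record or the episode. If it is the record, a recovery from Grade 2 to Grade 1 becomes one more event with a later onset.

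The tolerability profile over time is part of choosing a dose, which is a secondary objective. The sponsor already reasons from such quantities. The dose rationale (Protocol 4.4.1) describes the modified-release trial by counts of AEs: 101 in 9 subjects on orismilast, and 14 headaches of which 6 were at 40 mg. Protocol 4.2.2.4 and 4.3.1 rely on when AEs began: mostly in the first 4 weeks and very few after Week 8. Tables that mix new events with grade changes of old ones would blur both kinds of statement.

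**Working it through.** The plan gives no figure on this point, so there is none to reproduce. The check follows one episode through both documents and then gives the general formula.

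**1. One episode, assumed dates.** Nausea is Grade 1 from Day 3, Grade 2 from Day 6 and Grade 1 from Day 20, and resolves on Day 40. Each record is taken to end on the day the next begins.

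| | Counted as records | Counted as one episode |
|---|---|---|
| Events | 3 | 1 |
| Onset days | 3, 6, 20 | 3 |
| Starting in the initial 3 weeks (21 days) | 3 | 1 |
| Duration (end − start + 1) | 6−3+1 = 4; 20−6+1 = 15; 40−20+1 = 21; mean 40/3 = 13.3 days | 40−3+1 = 38 days |
| Patient count, SOC/PT table | 1 | 1 |
| Patient count, maximum-grade table | 1, at Grade 2 | 1, at Grade 2 |

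The last two rows do not change, because the SAP counts the patient once.

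**2. An event that eases after treatment.** A Grade 2 AE begins on treatment and falls to Grade 1 after the last dose. The Grade 1 record has an onset date in follow-up. Selected by that date, the patient enters the follow-up table although nothing new began. Counting the patient once does not correct the period.

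**3. General size.** Let q be the share of AEs that change grade over days and m the number of changes per such AE. Then records per episode = 1 + q × m. Both inputs are assumptions; the documents give neither.

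| q | m = 1 | m = 2 | m = 3 |
|---|---|---|---|
| 10% | 1.1 | 1.2 | 1.3 |
| 20% | 1.2 | 1.4 | 1.6 |
| 30% | 1.3 | 1.6 | 1.9 |
| 50% | 1.5 | 2.0 | 2.5 |

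**4. Difference between arms.** With equal true numbers of episodes and m = 2, assume q = 10% on placebo and 30% to 50% on active drug. The apparent active-to-placebo ratio of event counts is then between (1 + 2 × 0.3)/(1 + 2 × 0.1) = 1.6/1.2 = 1.33 and (1 + 2 × 0.5)/(1 + 2 × 0.1) = 2.0/1.2 = 1.67.

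One reason why q might differ is in Protocol Table 2. After Day 2 the daily total rises in 2 steps in the 20 mg arm (20-30-40), 4 in the 30 mg arm (20-30-40-50-60) and 6 in the 40 mg arm (20-30-40-50-60-70-80), with none on placebo. That makes a dose-related difference plausible but does not show one.

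**The case against.** The strongest reply is that the SAP never says each record is an event. Protocol 11.8.1 speaks of an event as distinct from its intensity, so the eCRF may hold intensity changes as a log under one parent AE. The eCRF design and the table shells are not in the documents, and either could contain a linking rule. This stands as far as it goes: a reader might infer that the tables are wrong, and the documents support only that their unit is undefined. It does not close the gap. SAP section 2 gives complete and appropriate methods as its purpose, and the protocol explicitly asks for distinct onset dates.

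Other stronger readings also fail:

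- Not every change of intensity makes a record. Changes more frequent than once a day are noted once, at the maximum.
- Protection is not confined to the maximum-grade tables. The count-once rule covers summaries by SOC and PT generally.
- A pretreatment AE that only improves after the first dose is not a TEAE under the stated definition, since it has neither begun nor worsened. It could be misflagged only if the definition were applied record by record.
- No AE table in the SAP's index is titled as reporting duration, so that exposure may be limited to other displays.
- The inflation rates are assumed. Some text points to less splitting: an AE of Grade 3 or higher ends study drug (Protocol 11.8.1), and the 2 participants with nausea at 40 mg or below in the modified-release trial had it for about 1 day (small numbers).
- Safety analyses are descriptive, and no stated dose-selection rule uses event counts.

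Finally, merging everything to first onset and maximum grade would do harm. Grade 1 diarrhoea from titration that becomes Grade 2 at Week 8 would appear only in titration, at Grade 2, and the by-grade table would lose its within-episode grades. This objection is sound, and the fix below is narrowed to meet it.

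**Conclusion.** The point holds as a gap between a stated recording rule and the tables built on it. Followed literally, the two documents count a recovery as a further event with a later onset. The outputs exposed are number of events, AE duration, TEAEs starting in the titration period, the five terms by time of onset, AEs and SAEs starting in follow-up, and any exposure-adjusted rate with an event numerator. Patient-level incidence by SOC and PT and by maximum grade is protected for AEs that begin on treatment.

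The size cannot be derived from the documents. Under assumed q of 10% to 50% and m of 1 to 3, event counts would be 1.1 to 2.5 times the number of episodes if records were counted uncollapsed. Whether the inflation rises with dose is conjecture. The efficacy analyses are untouched.

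**What to change.** Add one paragraph to SAP 12.1:

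1. Link consecutive records of the same patient and preferred term when the next record starts on the day the previous one ends or on the day after.
2. Count a linked episode once for number of events and for any event-based rate. State the numerator of the exposure-adjusted rates. Compute duration from first onset to final resolution.
3. A linked record of the same or a lower grade is never a new event, a new TEAE, or a new onset in the titration, time-of-onset or follow-up tables.
4. A linked record of a higher grade keeps its own date for TEAE status (worsening after the first dose). The onset-based tables show it as a worsening, separately from new onsets.
5. Keep the split records for the by-toxicity-grade table and the listings.

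The cost is the paragraph and one derivation step; sites and data collection do not change. The small downside is that two truly separate episodes with touching dates would be joined.
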